8.2 Eliciting and Reporting Adverse Events/Serious Adverse Events

Patients will be instructed to contact the Investigator at any time after ICF signature if any symptoms develop. At each study visit, patients will be asked a nonleading question to elicit any medically related changes in their well-being. Patients may also report AEs voluntarily and they will be instructed to contact the Investigator between visits if any symptoms develop or worsen.

AEs will be reported starting when the patient provides written informed consent. Clinically significant medical conditions present at the time of ICF signature will be reported as medical history. Clinically significant medical conditions that start or worsen after ICF signature will be reported as AEs.

All AEs, regardless of relationship to study treatment, will be reported from the time the patient signs the ICF until 30 days after the last dose of study treatment.

All SAEs, regardless of relationship to study treatment, will be reported from the date patient signs the ICF until at least 76 days after last dose of study drug, or start of new anticancer therapy, whichever is earlier; thereafter, only related SAEs will be reported.

Whenever possible, AEs should be reported as a diagnosis rather than individual signs and symptoms. If no diagnosis is available or has been identified, then the primary symptom is reported.

In general, the term ‘disease progression’ should not be used for reporting an AE/SAE. However, AEs/SAEs that are complications of disease progression should be reported.

All AEs reported or observed during the study will be recorded on the AE page of the eCRF. Information to be collected will include event term, date of onset, assessment of severity (Section 8.3), seriousness (Section 8.1), relationship to study treatment (Section 8.4), action taken with study treatment, date of resolution of the event or ongoing (when no resolution by the end of the reporting period), any required treatment or evaluations, and outcome.

New SAEs and any recurrent episodes, progression, or complications of the original SAE must be reported to the pharmacovigilance department of the Sponsor or delegate (e.g., contract

research organization [CRO]) within 24 hours after the time site personnel first learn about the event. Reporting will occur through the EDC system.

8.3 Assessment of Severity

The AEs will be graded according to CTCAE v5.0. For events not included in the CTCAE criteria, the severity of the AE is graded on a scale of 1 to 5 as shown in [Table 7](#).

Table 7. Definition of Severity Grades for CTCAE

Grade	Definition
1	Mild; asymptomatic or mild symptoms; clinical or diagnostic observations only; intervention not indicated.
2	Moderate; minimal, local or noninvasive intervention indicated; limiting age-appropriate instrumental activities of daily living (ADL). ^a
3	Severe or medically significant but not immediately life threatening; hospitalization or prolongation of hospitalization indicated; disabling; limiting self-care ADL. ^b
4	Life-threatening consequences; urgent intervention indicated.
5	Death related to adverse event.

^a ADL refers to preparing meals, shopping for groceries or clothes, using the telephone, managing money, etc.

^b Self-care ADL refers to bathing, dressing and undressing, feeding self, using the toilet, taking medications, and not bedridden.

The AEs characterized as intermittent do not require documentation of onset and duration of each episode.

8.4 Assessment of Causality

The Investigator's assessment of an AE's relationship to study treatment is an important part of safety reporting, but is not a factor in determining whether an AE is reported. An AE will be assessed as related to study treatment if there is a reasonable possibility of causal relationship with the use of the study treatment. For SAEs, whenever possible, the Investigator should provide a rationale for the causality assessment.

The investigator or qualified subinvestigator is responsible for providing an assessment of the relationship to the study drug(s) using clinical judgment and the following considerations:

Causality	Definition
Not related	An adverse event is not related to the study drug
Unlikely related	An adverse event where evidence exists for an alternative explanation other than the study drug e.g concomitant medication(s), concomitant disease(s), or time to onset suggests unlikely relationship.
Possibly related	An adverse event that might be due to study drug. An alternative explanation (e.g concomitant medication(s), concomitant disease(s), or time to onset) is inconclusive, where a causal relationship with study drug cannot be ruled out.
Probably related	An adverse event that might be due to study drug. An alternative explanation (e.g concomitant medication(s), concomitant disease(s)) is less likely, and where a causal relationship with study drug is more suggestive (ie time to onset, positive dechallenge/rechallenge).
Related	An adverse event where an alternative explanation cannot be explained and, therefore, considered related to study drug.

8.5 Special Situations Reports

8.5.1 Definitions of Special Situations

Any special situation occurring in a participant that may require expedited reporting or safety review may include the following with the study drug:

- Pregnancy reports (see [Section 8.5.2](#))
- Overdose reports (see [Section 8.5.3](#))
- Other special situations (see [Section 8.5.4](#)), such as:
 - Suspected misuse or abuse
 - Accidental exposure
 - Medication error
 - Exposure to the study drug from breast-feeding
 - Adverse events associated with product complaints

8.5.2 Reporting Pregnancy

Any pregnancy in a participant that occurs from the time the patient signs the ICF up to 9 months after discontinuation of loncastuximab tesirine or up to 1 months after terminating idelalisib treatment during the study must be reported using the Pregnancy Report Form. Any pregnancy in a partner of a male participant that occurs from signing the ICF up to 6 months

post last loncastuximab tesirine or up to 3 months post last idelalisib during the study must be reported. Pregnancy must be reported within 24 hours after the site personnel first learn of the pregnancy. The pregnancy itself is not considered an AE. However, the pregnancy must be followed to determine outcome (including spontaneous miscarriage, elective termination, normal birth, or congenital abnormality) and status of mother and child, even if the patient discontinued from the study. Abortions (elective or spontaneous) occurring during the pregnancy reporting period must be reported as an SAE.

Any SAE occurring in association with a pregnancy that is brought to the Investigator's attention after the patient has completed the study and considered by the Investigator as possibly related to the study treatment must be promptly reported in the same manner.

Once pregnancy is confirmed in a study participant, study treatment will be discontinued, see [Section 7.4.6](#) for additional information.

8.5.3 Reporting Overdose

An overdose of the study drug(s) is defined under [Section 6.6](#).

An overdose itself is not considered an AE. However, if such an overdose occurs during the study, with or without any signs or symptoms, it must be reported to ADC Therapeutics within 24 hours after the time site personnel first learn about the event.

8.5.4 Reporting Other Special Situations

All other special situation reports must be reported within 24 hours after the time site personnel first become aware of the situation.

9 Statistical Considerations

Full details of the analysis plan, including a more technical and detailed elaboration of the statistical analyses, will be provided in the statistical analysis plan (SAP).

9.1 Sample Size Determination

Approximately 150 patients will be enrolled and randomly assigned to treatment with loncastuximab tesirine or idelalisib in a 2:1 ratio. The study is over-powered for the primary efficacy endpoint when a 55% of CRR in loncastuximab tesirine (compared to observed 64.3% CRR in Phase 1 trial) and 15% from idelalisib ([Salles G, 2017](#)) are assumed. The purpose of a larger sample size and 2:1 randomization ratio is to provide a more robust safety data set (~100 FL patients treated with loncastuximab tesirine). [Table 8](#) and [Table 9](#) summarizes the study power when different CRR and ORR are expected.

Table 8. Power for Primary Endpoint CRR with 2-Sided Significance Level 0.05

Expected CRR from loncastuximab tesirine arm*	55%	45%	40%
CRR from idelalisib arm**	15%	15%	15%
Power***	99%	96.1%	87.3

* Data from Phase 1 trial (ADCT-402-101) shows that CRR is approximately 64%, lower CRRs are assumed in this study

** CRR from idelalisib is assumed to be 15% ([Salles G, 2017](#))

*** Based on nquery fisher's exact test

Table 9. Power for Key Secondary Endpoint ORR with 2-Sided Significance Level 0.05

Expected ORR from loncastuximab tesirine arm*	79%	75%	70%
ORR from idelalisib arm**	54%	54%	54%
Power***	84.1%	67.3%	41.7%

* Data from Phase 1 trial (ADCT-402-101) shows that ORR is approximately 79%.

**ORR from idelalisib is assumed to be 54% ([Idelalisib® US- Prescribing Information](#)).

*** Based on nquery fisher's exact test

9.2 Analysis Populations

- Intent-to-treat (ITT) Population: All patients who are randomized. This population will be used in the primary analyses of efficacy.
- All-Treated Population: All patients who receive at least 1 dose of loncastuximab tesirine or idelalisib. This population will be used in the primary analyses of safety.
- Per-Protocol Population: All patients in the all-treated population without important protocol deviations, which will be further described in detail in the SAP.
- The PK Population: All patients who receive loncastuximab tesirine and have at least 1 pre-(C1D1) and 1 post dose valid assessment.
- The Immunogenicity Population: All patients who receive loncastuximab tesirine and have at least 1 valid ADA assessment.
- The Pharmacodynamic Population: All patients who receive study drug and have at least 1 valid pharmacodynamics/ [REDACTED]
- Patient-reported Outcomes Population: All patients who receive at least 1 dose of study treatment and complete at least one questionnaire at baseline and at one postbaseline visit.

9.3 Interim Analysis

A non-binding futility analysis on the primary endpoint of CRR will be performed for the first 60 patients (40% patients) around 12 weeks after the 60th patient is randomized (enough time for 2 disease assessments). O'Brien-Fleming spending function as the non-binding lower bound (futility) will be used. The details will be provided in SAP.

9.4 Final Analysis

For primary and key secondary endpoint analyses, a database snapshot will be taken 12 months after last patient is randomized in order to allow approximately 9 months of duration of response follow up. All efficacy and safety endpoints will be analyzed and reported in the clinical study report (CSR).

Results of the population PK analysis will be reported separately.

The CR rate will be tested in the intent-to-treat population between two treatment arms by using Cochran–Mantel–Haenszel (CMH) method adjusted by stratification factors from randomization list. The point estimates for odds ratio and difference in CRR with 95% confidence interval (CI) will be presented. If CRR is significantly different between two arms, the key secondary endpoint ORR will be sequentially tested using the same approach as CRR.

The PFS and OS analysis will be performed using PROC LIFETEST adjusted by stratification factor from randomization list. Kaplan-Meier plot for PFS, OS, and DOR will be presented by treatment.

Follow-up analyses will be performed when all the patients complete the study per protocol. The results will be reported as CSR addendum.

9.5 Demographics and Baseline Characteristics

Demographics and Baseline characteristics, such as cancer history and medications history, will be summarized for the ITT Population.

The Follicular Lymphoma International Prognostic Index (FLIPI) ([Solal-Celigny P, 2004](#)) will be calculated based on 5 clinical and laboratory parameters (age, Ann Arbor stage, number of nodal areas, LDH, and hemoglobin level) derived from baseline visit. In case required data point is missing for the baseline visit, then data from the screening visit will be used.

9.6 Exposure to Treatments

Exposure to study treatment, prior, and concomitant medications will be summarized for the All-treated Population. Dose interruptions, reductions, and relative dose intensity will also be summarized.

9.7 Efficacy Analyses

Efficacy analyses will be based on disease assessment by central review. The primary efficacy analysis will be CRR analysis, and ORR will be a key secondary endpoint. Additional secondary efficacy analyses will include analyses of PFS, OS, and DOR.

Response reported by investigators (CRR, PFS, ORR, DOR) will be used for sensitivity analyses.

When best overall response (BOR) is determined, in contrast to CR, PR, or PD, a BOR of SD can only be made after the patient is on-study for a minimum of 35 days after the first dose of study treatment. Any tumor assessment indicating SD before this time period will be considered as a non-evaluable for BOR if no assessment after this time period is available.

9.7.1 Complete Response Rate

Complete Response Rate assessed according to the 2014 Lugano classification will be defined as the proportion of patients with a BOR of CR, based on response assessments obtained prior to any subsequent cancer treatment. The percentage of CRR with its 95% CI will be presented. For the primary CRR and secondary ORR analysis in the ITT population, patients with missing response or not evaluable information will be counted as failures.

The CR rate will be tested in the ITT population between two treatment arms by using CMH method adjusted for stratification factor in randomization list. The point estimates for odds ratio and difference in CRR with 95% CI will be presented.

A sensitivity analysis using exact method for CRR without adjusting for the covariate will also be performed. In addition, CRR will be analyzed using CMH method adjusted for prognostic baseline covariates (e.g., age, disease characteristics, FLIPI, region etc.) in the sensitivity analysis. If there are continuous variables, logistics regression may be used.

9.7.2 Overall Response Rate

The ORR will be defined as the proportion of patients with a BOR of CR or PR. The overall response category will be derived based on response assessment performed on or before the start of subsequent anti-cancer therapy. For the primary ORR analysis in the all-treated population, patients with a CR or PR will be counted as successes and all other patients (including those with missing response information) will be counted as failures. The ORR will be tested in the ITT population by using the same approach as primary analysis and it will be tested only after primary analysis is significant. Similar sensitivity analyses will be performed for primary endpoint.

9.7.3 Progression-Free Survival

The PFS will be defined among ITT patients as the time from randomization date until the first date of either disease progression or death due to any cause. The date of disease progression will be defined as the earliest date of disease progression based on central review. For patients whose disease has not progressed at the time of the analysis, censoring will be performed using the date of the last valid disease assessment prior to initiation of a new anticancer therapy including Hematopoietic Stem Cell Transplantation (HSCT). Stratified Log-rank testing will be used to compare PFS between the 2 treatment arms. The hazard ratio along with the 95% confidence interval (CI; 2-sided) will be estimated using the stratified Cox model with treatment as the explanatory variable. The stratification factor from the randomization list will be used. The Kaplan-Meier (K-M) survival curves, 25th, 50th (median), 75th percentiles (if estimable), and survival probability at 0.5, 1, and 2 years along with the 2-sided 95% CIs will also be provided for each treatment group. Further details will be outlined in the SAP.

A sensitivity analysis of PFS will be conducted in which the PFS for patients undergoing HSCT will not be censored at HSCT.

In addition, a stratified Cox regression model may be used to further evaluate the treatment effects on PFS after adjusting for some prognostic factors. Besides treatment and the stratification factor from the randomization list, the following prognostic factors may be included in the model simultaneously: age, race (white, non-white), baseline ECOG score, FLIPI, baseline cancer stage. [REDACTED]

9.7.4 Overall Survival

Median OS will be defined as the time from the randomization date until death due to any cause. For patients who have not died at the time of the analysis, censoring will be performed using the date the patient was last known to be alive. Stratified Log-rank testing will be used to compare OS between the 2 treatment arms. The hazard ratio along with the 95% confidence interval (CI; 2-sided) will be analyzed by using stratified Cox model with treatment as the explanatory variable. The stratification factors from randomization list will be used. The median OS time, The Kaplan-Meier (K-M) survival curves, 25th, 50th (median), 75th percentiles (if estimable), and survival probability at 0.5, 1, and 2 years along with the 2-sided

95% CIs will also be provided for each treatment group. Further details will be outlined in the SAP.

A stratified Cox regression model may be used to further evaluate the treatment effects on OS after adjusting for some prognostic factors. Besides treatment and the stratification factors from the randomization list, the following prognostic factors may be included in the model simultaneously: age, race (white, non-white), baseline ECOG score, FLIPI, baseline cancer stage. [REDACTED]

9.7.5 Duration of Response

The DOR will be defined among responders (CR or PR) as the time from the earliest date of first response until the first date of either disease progression or death due to any cause. The date of disease progression will be defined as the earliest date of disease progression based on central review. For patients who have not progressed or died at the time of the analysis, censoring will be performed using the date of the last valid disease assessment prior to initiation of a new anticancer therapy (including HSCT). The Kaplan-Meier plot, median DOR and 95% CI will be presented by treatment. Further details will be outlined in the SAP. A sensitivity analysis of DOR will be conducted in which the DOR for patients undergoing HSCT will not be censored at HSCT.

9.7.6 Subgroup analysis

Subgroup analyses such as age, gender, region and other important baseline characteristics may be conducted for CRR, ORR, PFS, OS and DOR.

9.8 Safety Analyses

Safety analyses will be presented descriptively.

9.8.1 Adverse Events

The focus of AE summarization will be on TEAEs. A TEAE is defined as an AE that occurs or worsens in the period extending from the first dose of study treatment until 30 days after the last dose of study treatment or start of new anti-cancer therapy, whichever is earlier.

All TEAEs will be summarized. Summary tables will be presented to show the number of patients reporting TEAEs by severity grade and corresponding percentages. A patient who reports multiple TEAEs within the same Preferred Term (or System Organ Class) is counted only once for that Preferred Term (or System Organ Class) using the worst severity grade.

Separate summaries will be prepared for TEAEs classified as severe or life-threatening (\geq Grade 3); study treatment-related AEs; AEs leading to treatment interruption, modification, or discontinuation; SAEs; and death.

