1.2.3 Clinical Study Data for Loncastuximab Tesirine and Idelalisib

Loncastuximab tesirine

ADCT-402-101 (NCT02669017, <https://clinicaltrials.gov/ct2/show/NCT02669017>), was a first-in-human Phase 1 dose-escalation study of loncastuximab tesirine in R/R B-cell NHL patients. The data from this study showed loncastuximab tesirine exhibits significant anti-tumor activity in heavily pretreated patients with R/R FL, with an ORR of 78.6% and a CRR of 64.3%. Median duration of response and median progression free survival (PFS) were both not reached.

Toxicity was manageable, with the most common Grade ≥ 3 treatment-emergent adverse events (TEAEs) being Gamma-glutamyl transferase (GGT) increased (21.3%); neutropenia (16.9%); anemia (15.3%); neutrophil count decreased (14.8%); thrombocytopenia (12.0%); platelet count decreased (10.4%); blood alkaline phosphatase (ALP) increased (6.6%); lymphocyte count decreased (6.6%); disease progression (6.0%); febrile neutropenia (5.5%); and hypokalemia (5.5%) ([Loncastuximab tesirine IB](#))

Idelalisib

Idelalisib is the only PI3K inhibitor approved by FDA and EMA as monotherapy for the treatment of adult patients with FL that is R/R to two prior lines of treatment.

In Study 101-09 (NCT01282424, <https://clinicaltrials.gov/ct2/show/NCT01282424>), 72 patients with FL received 150 mg of idelalisib orally twice (BID) daily until evidence of disease progression or unacceptable toxicity. The ORR was 55.6% and CRR was 16.7%. The median PFS was 11.0 months (range 8.0–14.0), and the median DOR was 11.8 months (range 6.2–26.9) ([Idelalisib -SmPC](#)).

The most common Grade ≥ 3 TEAEs in 125 adults with indolent non-Hodgkin lymphoma treated with idelalisib 150 mg BID in clinical trials were elevated transaminases (21%), diarrhea (13%), neutropenia (27%), pneumonia (7%), and thrombocytopenia (6%) (Gopal et al, 2014).

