4.3 Study Stopping Rules

Once at least 15 patients have been treated with idelalisib, study enrollment will be paused for safety evaluation if any of the following occur:

1. The number of patients with reported Grade 5 toxicity in the loncastuximab tesirine arm is more than twice the number of patients with reported Grade 5 toxicity in the idelalisib arm.
2. Grade 4 skin toxicity is reported in >2 patients treated with loncastuximab tesirine and the incidence of Grade 4 skin toxicity in patients treated with loncastuximab tesirine is >5% and the incidence is at least 50% higher than the incidence in patients treated with idelalisib.
3. Grade 4 toxicity of edema or effusion is reported in >2 patients treated with loncastuximab tesirine and the incidence of Grade 4 toxicity of edema or effusion in patients treated with loncastuximab tesirine is >5% and at least 50% higher than the incidence in patients treated with idelalisib.

Safety evaluation will be performed by ADCT.

5 Patient Population

Patients must meet all inclusion criteria and none of the exclusion criteria to be eligible for the study. All criteria have to be assessed during Screening, unless otherwise specified.

Prospective approval of protocol deviations to recruitment and enrollment criteria, also known as protocol waivers or exemptions, is not permitted.

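### TEAE tables count by single Preferred Term; neutropenia and thrombocytopenia, each split over two terms in Phase 1, need pre-specified grouped rows

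*Combined protocol and SAP*

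**What the plan says.** Section 9.8.1 (Adverse Events) gives the rule for TEAE tables: "A patient who reports multiple TEAEs within the same Preferred Term (or System Organ Class) is counted only once for that Preferred Term"; the same holds within a System Organ Class, and the worst grade is used. The section also promises separate summaries of events of Grade 3 or higher, treatment-related events, events leading to interruption, modification or discontinuation of treatment, SAEs, and deaths. It names no grouped or combined terms, and neither does any other section of the protocol.

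Section 1.2.3 introduces the Phase 1 list with "the most common Grade ≥ 3 treatment-emergent adverse events (TEAEs) being". The list includes "neutropenia (16.9%); anemia (15.3%); neutrophil count decreased (14.8" and "thrombocytopenia (12.0%); platelet count decreased (10.4" (all percentages). Each cytopenia therefore appears twice, once as a diagnosis and once as a laboratory finding.

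Three other provisions bear on the point:

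- Sections 8.1.3 and 8.2 ask sites to prefer a diagnosis to a laboratory result or a symptom.
- Section 9.8.2 plans shift tables of gradable laboratory results by CTCAE grade, with worst-case post-baseline summaries.
- The opening of Section 9 leaves full analysis details to the SAP.

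**The concern.** A patient with a low neutrophil count can be recorded under either term. If sites divide between the two, Section 9.8.1 yields two rows and neither gives the proportion of patients affected. The two rows cannot simply be added, because some patients may be in both. A System Organ Class row does not isolate the cytopenia either, since it collects other terms as well.

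This matters more than usual here because Sections 2.1 and 9.1 say that the sample size was set to provide safety data on about 100 loncastuximab tesirine patients. A reader of the clinical study report will want the proportion with neutropenia or thrombocytopenia, and the proportion in whom it was related, serious, or led to a dose action. As written, the AE tables may not supply those proportions.

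**Working it through.** The plan states no figure to reproduce: safety is descriptive, with no power or alpha. The check is a bound on the union of two terms.

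**Inputs** (Section 1.2.3, Phase 1, Grade 3 or higher): neutropenia a = 16.9%, neutrophil count decreased b = 14.8%; thrombocytopenia a = 12.0%, platelet count decreased b = 10.4%. The overlap o (patients with both terms) is not given, so it is varied from 0 to b.

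**Can the percentages be added?** Only if they share a denominator. Among denominators from 20 to 399, only 183 and its multiple 366 reproduce all eleven listed percentages, which is consistent with one common safety population.

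**Formulas.** Patients with either term: U = a + b − o. Understatement by the larger row: 1 − a/U.

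| Share of smaller term that overlaps | Neutropenia: U | Understated by | Thrombocytopenia: U | Understated by |
|---|---|---|---|---|
| 0% | 16.9 + 14.8 = 31.7% | 1 − 16.9/31.7 = 46.7% | 12.0 + 10.4 = 22.4% | 1 − 12.0/22.4 = 46.4% |
| 50% | 31.7 − 7.4 = 24.3% | 30.5% | 22.4 − 5.2 = 17.2% | 30.2% |
| 100% | 31.7 − 14.8 = 16.9% | 0% | 22.4 − 10.4 = 12.0% | 0% |

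A reader who looks only at the smaller row is further off: 12.4% (1 − 14.8/16.9) to 53.3% (1 − 14.8/31.7) for neutropenia, and 13.3% (1 − 10.4/12.0) to 53.6% (1 − 10.4/22.4) for thrombocytopenia.

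**Does it change a reading within Phase 1?** The list is headed by "Gamma-glutamyl transferase (GGT) increased (21.3" per cent. Combined neutropenia would exceed that unless the overlap is at least 31.7 − 21.3 = 10.4 points, or 10.4/14.8 = 70% of the smaller term. The order of the list therefore depends on an overlap that single-term rows do not show.

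**Which summaries are affected?** Laboratory shift tables count measured values and carry no investigator judgement of relatedness, no seriousness flag and no action taken. Table 4 holds loncastuximab tesirine for neutropenia or thrombocytopenia of Grade 3 or higher, and Section 8.1.3 requires a laboratory abnormality that leads to interruption to be recorded as an AE. Such events will enter the dose-action summary, where only the term-based rows exist.

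**The case against.** The strongest reply is Section 9.8.2. Neutrophils and platelets are in the hematology panel (Section 7.4.5), so the grade-shift and worst-case tables give cytopenia severity per arm whatever term a site chose. That stands for overall frequency. It does not reach the related, serious and dose-action summaries. The laboratory tables are also not ascertained alike in the two arms: scheduled hematology falls on Day 1 of 3-week cycles under loncastuximab tesirine, and on Days 1 and 15 of 4-week cycles through Cycle 7 under idelalisib (Tables 1 and 2).

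Second, Sections 8.1.3 and 8.2 steer sites towards diagnoses, and nothing says whether Phase 1 worked under the same rule. Splitting may therefore be less frequent here. But the rule in Section 8.1.3 applies only where the abnormality fits a clinical diagnosis, its one example is anemia, it relies on site compliance, and no analysis step recombines terms if both are entered.

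Third, detail is deferred to the SAP. No separate SAP text accompanies the protocol sections examined here, so a grouping rule may exist there. Unlike Sections 9.8.2 and 9.8.3, Section 9.8.1 contains no deferral of its own; it states a rule that can be followed as it stands.

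Three stronger readings are tempting and are not supported:

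- *The drug's main toxicities are understated by half.* Only two toxicities are shown split. GGT increased (21.3%) and anemia (15.3%) are not. The ceiling near 47% needs zero overlap, and both rows of each pair would still be printed.
- *The ranking against idelalisib reverses.* Section 1.2.3 gives idelalisib "neutropenia (27%), pneumonia (7%), and thrombocytopenia (6" per cent, and 27% lies inside 16.9% to 31.7%. That is a comparison across studies with different populations, and Phase 1 was dose-escalation in mixed B-cell NHL. The protocol does not say how the idelalisib terms were counted. Here one rule applies to both arms, so no direction of between-arm bias follows.
- *The stopping rules cannot be operated.* Section 4.3 sets patient-level counts, for example "Grade 4 toxicity of edema or effusion is reported in >2 patients treated with loncastuximab tesirine", which the sponsor evaluates during enrollment. They do not depend on the tables of Section 9.8.1.

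**Conclusion.** The point holds as a modest reporting gap with a cheap remedy. Followed as written, Section 9.8.1 can produce AE rows from which the patient-level rate of neutropenia or thrombocytopenia cannot be recovered. At Phase 1 rates that rate would lie between 16.9% and 31.7%, and between 12.0% and 22.4%, so the larger single row would be too low by 0% to about 47%.

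This rests on three assumptions: that terms split here as they did in Phase 1, that overlap may lie anywhere between none and full, and that the SAP does not already group these terms. No test, error rate or efficacy conclusion is affected, because safety analyses are descriptive (Section 9.8). Laboratory tables cover part of the gap; the related, serious and dose-action summaries remain exposed.

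**What to change.** In Section 9.8.1, and correspondingly in the SAP:

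- Define grouped terms for at least neutropenia with neutrophil count decreased, and thrombocytopenia with platelet count decreased.
- Count each patient once per group, at worst grade, by the same rule in both arms.
- Show the grouped rows in every TEAE summary, including the treatment-related, serious, and interruption, modification or discontinuation tables.
- Keep the single-term rows alongside.

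Fix the list before the safety data are reviewed, because a grouping chosen afterwards in an open-label trial is open to challenge. If the SAP already contains such a list, a cross-reference from Section 9.8.1 is enough.

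The cost is a short list and one extra set of rows. Reported cytopenia AE rates may look less favourable than the single-term rows. Sample size, data collection and site procedures do not change.
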